5. STUDY DESIGN

5.1. Overall Design

- This is a randomized, double-blind, active-controlled, parallel-group, multi-center study in hemodialysis-dependent participants, including combination methods such as hemodiafiltration or hemofiltration with HD, who have anemia of CKD and are currently treated with rhEPO or its analogs.
- This study includes a 4-week Screening Period, a 52-week Treatment Period and a Follow-up Period (Figure 1).
- The 52-week Treatment Period consists of:
 - The Stabilization Period (SP), defined as the period from Day 1 to Week 28 (up to but excluding the Week 28 visit), during which study treatment will be dose-titrated to achieve and maintain Hgb in the target range.
 - The Evaluation Period (EP), defined as the period from Week 28 to Week 52, to assess long-term efficacy and safety. The study treatment may be dose-titrated, if needed, during this period to achieve or maintain Hgb level in the target range.

Figure 1 Study Schematic

- Each participant will remain in the study for up to 62 weeks. Participants who permanently discontinue study treatment will remain in the study.

- Randomization will be stratified by region (see [Appendix 7](#)). Following stratification, participants will be randomized 2:1 to daprodustat or epoetin alfa. Daprodustat will be administered three-times weekly and epoetin alfa will be administered once weekly or three-times weekly, depending on dose level (Section 7).
- Due to the difference in formulations between the investigational product and active control (tablets versus IV injection), and in order to maintain the study blind, each participant will receive a tablet and an IV study treatment; one will be active and one will be inactive (Section 7). Participants randomized to receive daprodustat will also receive saline IV injection. Participants randomized to receive epoetin alfa will also receive placebo tablets.
- PK samples will be collected from all study participants to enable exposure-response and exposure-safety analyses (Section 9.5).
- Adjustment of both study treatments (tablet and IV injection formulations) will follow a protocol-specified study treatment dose adjustment algorithm to achieve and maintain Hgb within the target range of 10.0 to 11.0 g/dL, inclusive (Section 7.2). Dose changes will be made programmatically by the Interactive Response Technology (IRT) system for both study treatment arms.

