5.2. Number of Participants

A sufficient number of participants, which is expected to be approximately 800 participants, will be screened to achieve approximately 402 randomized participants (268 to daprodustat and 134 to epoetin alfa) and approximately 360 evaluable participants (i.e., participants with at least one evaluable Hgb assessment during the EP).

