**7.2. Principal Secondary Efficacy Analyses****7.2.1. Endpoint / Variables**

Average monthly IV iron dose (mg)/participant to Week 52

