**7.2.5.1. Statistical Methodology Specification**

Endpoint / Variables

 
• Average monthly IV iron dose (mg)/participant to Week 52
 

Model Specification

 
• Average monthly IV iron dose (mg)/participant to Week 52 will be determined by calculating the total IV iron dose per subject from Day 1 to Week 52 while the participant was on study treatment and dividing by (the number of days the participant was on study treatment/30.4375 days). See Section 14.4.1 for the definition of on-treatment IV iron.
 
• An ANCOVA model will be used to compare the difference in average monthly IV iron dose per participant between arms, adjusting for: 
 
○ Treatment
 
○ Baseline monthly IV iron dose (see Section 5.2.1)
 
○ Region (as randomized, see Section 5.3 & Section 5.4.1)
 
 
 

Model Results Presentation

 
• The number and percentage of subjects with baseline IV iron use, on-treatment EP IV iron use, and on-treatment IV iron use to Week 52 will be summarized by treatment. Boxplots by study treatment will be created separately for on-treatment average monthly IV iron dose to week 52 and for post-randomization average monthly IV iron dose to week 52.
 
• Average monthly IV iron dose at baseline, while on treatment during the EP, and while on treatment to Week 52 will be summarized by treatment group using mean, standard deviation, minimum, P25, median, P75, and maximum.
 
• The least square (LS) mean estimates and standard errors by treatment group, LS mean difference, two-sided 95% CI and one-sided superiority p-value for the difference in average monthly IV iron dose/subject to Week 52 between the daprodustat and rhEPO arms from the ANCOVA model will be presented. The number of subjects contributing to the analysis and the associated mean and standard deviation of the baseline and Week 52 values will also be displayed with the results of the ANCOVA model.
 
• A listing of average monthly IV iron dose will be provided including treatment, site ID, unique subject ID, subject ID, time period, and average monthly IV iron dose at Week 52.
 

Model Results Interpretation

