
 
• Conditional on the primary endpoint achieving non-inferiority at the one-sided 2.5% level, statistical testing will progress to the principal secondary endpoint with a focus on superiority using a one-sided 2.5% significance level.
 

Supportive Statistical Analyses
Average monthly IV iron dose (mg)/subject to Week 52 using on and off treatment IV iron records

 
• The summaries and analysis described above for the principal secondary average monthly IV iron dose/subject to Week 52 will be repeated using all available IV iron records during the Day 1 – Week 52 visits, regardless of whether or not a subject was on treatment (i.e. treatment policy estimand).
 
• The average monthly IV iron dose (mg)/subject to Week 52 for this analysis will be determined by calculating the total IV iron dose per subject from Day 1 to Week 52 and
 

Supportive Statistical Analyses
dividing by (earliest of the (Week 52 visit date, study completion/withdrawal date) – Randomization date + 1 day/30.4375 days).
Subgroup Analysis

 
Subgroup analyses will be performed for the principal secondary endpoint using ANCOVA model with terms for treatment group, baseline IV iron dose, region, subgroup and treatment by subgroup interaction. Subgroup analysis details are discussed in Section 5.4.2.
 
Subgroup analysis results will be presented graphically using a forest plot.
 

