**Standardized IV Iron Dose (mg/month) from Randomization to Week 52**

- In order to calculate the average monthly IV iron dose from Randomization to Week 52, the dose of IV iron will be standardized to obtain a continuous single unit IV iron dose in terms of mg/month for the period from the Randomization date to the Week 52 visit date while the subject is on treatment.
  - Note: Subjects who are randomized but never treated will not have a value for average monthly IV iron from Randomization to Week 52.
- IV iron therapy concomitant medication records that occur or are ongoing during the period from the subject's (Randomization date – 12 weeks) to the Week 52 visit date will be selected and ordered by start date and end date.
- The standardization will be carried out with the following formula:
  - Standardized IV iron dose (mg/week) = IV iron drug dose (mg) \* frequency

Note: Frequency and Gap Factors defined as follows:

Frequency (from eCRF)	Frequency (for standardization formula)	Gap Factor
2 times per week	2	2.5 days
3 times per week	3	1.33 days
4 times per week	4	0.75 day
5 times per week	5	0.4 day
BID	14	0 days
Once daily	7	0 days
One time dose	1	n/a
Every 12 Hours	14	0 days
Every 2 weeks	0.5	13 days
Every 4 weeks	0.25	27 days
Once a month	0.23	29 days
Once a week	1	6 days
TID	21	0 days

- If the frequency of the record is not 'one time dose', then duration is calculated as follows:

CONFIDENTIAL

204837

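### The IV iron ANCOVA pools variance under 2:1 allocation with no variance check, so its 95% CI is too narrow if the daprodustat SD is the smaller one

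*SAP*

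**What the plan says.** The endpoint is "Average monthly IV iron dose (mg)/participant to Week 52" (SAP 7.2.1). SAP 7.2.5.1 forms it for each participant from total on-treatment IV iron, "dividing by (the number of days the participant was on study treatment/30.4375 days". On the analysis it says: "An ANCOVA model will be used to compare the difference in average monthly IV iron dose per participant between arms". Besides the treatment term, the covariates are the baseline monthly dose and region. The outputs are the "LS mean difference, two-sided 95% CI and one-sided superiority p-value for the difference in average monthly IV iron dose/subject to Week 52". If the primary endpoint passes, the test is for "superiority using a one-sided 2.5% significance level". It is the only other test under multiplicity control (SAP 5.5).

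On allocation, Protocol 5.1 says: "Following stratification, participants will be randomized 2:1 to daprodustat or epoetin alfa". Protocol 5.2 plans "402 randomized participants (268 to daprodustat and 134 to epoetin alfa". Almost everyone contributes a value. SAP 14.6.3.2 excludes only the untreated: "Subjects who are randomized but never treated will not have a value for average monthly IV iron from Randomization to Week 52".

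Neither SAP 7.2.5.1 nor Protocol 10.3.1 names a variance structure for this model. Equal residual variance is therefore implied by a plain ANCOVA rather than written down. The residual plots, the constant-variance check and the fallback to transformed data appear in SAP 7.1.5.1, for the primary haemoglobin model only. The supportive iron analysis, which uses on- and off-treatment records, repeats the same ANCOVA.

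**The concern.** A plain ANCOVA estimates one residual variance from both arms, and the larger arm dominates that estimate. With 2:1 allocation, a smaller spread on daprodustat pulls the pooled variance down. The uncertainty in the difference, however, comes mainly from the smaller and more variable epoetin arm, so the standard error is too small and the interval too short.

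This direction is plausible for a dose outcome. It is bounded at zero, non-users can sit at zero, and if daprodustat scales doses down, the spread falls with them. The interval would then be least reliable in the case the sponsor hopes for. What is at stake is the stated precision of the effect estimate on a confirmatory endpoint.

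**Working it through.** **The plan's own figure.** The documents give no power, SD or CI width for IV iron. The only stated precision is for haemoglobin (Protocol 10.1.1), and it reproduces: with SD 1.5 g/dL and 240:120 evaluable, 1.96 × 1.5 × √(1/240 + 1/120) = 0.329, against 0.33 stated. The largest difference meeting non-inferiority is −0.75 + 0.329 = −0.421, against −0.42 stated.

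**Inputs for IV iron.** n_T = 268 and n_C = 134 (Protocol 5.2). The ratio r = residual SD on daprodustat / residual SD on epoetin is assumed, over 0.5 to 1.25.

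**Formula.** Setting the epoetin SD to 1:

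- pooled variance: s² = [(n_T − 1)r² + (n_C − 1)] / (n_T + n_C − 2)
- SE ratio (pooled/true): R = √{ s²(1/n_T + 1/n_C) / (r²/n_T + 1/n_C) }
- coverage: 2Φ(1.96R) − 1

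Worked at r = 0.8: s² = (267 × 0.64 + 133)/400 = 0.760. The pooled variance of the difference is 0.760 × 0.01119 = 0.00850. The true variance is 0.64/268 + 1/134 = 0.00985. So R = √(0.00850/0.00985) = 0.929, and coverage is 93.1%.

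| r | SE ratio R | Coverage of nominal 95% CI | Change in CI width if corrected (1/R − 1) |
|---|---|---|---|
| 0.5 | 0.816 | 89.0% | +22% |
| 0.7 | 0.891 | 91.9% | +12% |
| 0.8 | 0.929 | 93.1% | +7.6% |
| 0.9 | 0.966 | 94.2% | +3.5% |
| 1.0 | 1.000 | 95.0% | 0 |
| 1.1 | 1.032 | 95.7% | −3% |
| 1.25 | 1.076 | 96.5% | −7% |

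With 1:1 allocation (201:201), R = 1.000 at every r, so the effect comes from the 2:1 ratio.

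**Does a lower mean imply r below 1?** It depends on how the mean falls. Suppose a share p of participants uses iron, with coefficient of variation c among users. The variance is then proportional to p(1 + c² − p).

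- Every dose scaled by 0.8: r = 0.80.
- Users fall from 80% to 65%, c = 0.5: r = √[(0.65 × 0.60)/(0.80 × 0.45)] = √(0.390/0.360) = 1.04.
- Same fall in users, c = 1: r = √[(0.65 × 1.35)/(0.80 × 1.20)] = 0.956.

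Fewer users lowers the SD only while p is below (1 + c²)/2.

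**Simulation check.** The ANCOVA was simulated with baseline dose and five regions, 268:134, 8,000 trials per scenario and assumed skewed doses with zeros.

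| Scenario | r | Model-based coverage | Robust (HC2) coverage |
|---|---|---|---|
| No effect, same distribution | 1.00 | 94.6% | 94.7% |
| All doses × 0.9 | 0.90 | 93.9% | 94.6% |
| All doses × 0.8 | 0.80 | 93.2% | 94.8% |
| All doses × 0.7 | 0.70 | 92.2% | 94.9% |
| 20% fewer users, c = 0.5 | 1.00 | 95.5% | 95.4% |
| 20% fewer users, c = 1 | 0.94 | 94.7% | 94.9% |

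Monte Carlo error is about √(0.95 × 0.05/8,000) = 0.24 percentage points, so the results agree with the formula.

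**The case against.** **The condition is the SD, not the mean.** A reader might infer that any fall in iron use makes the interval too narrow. The documents do not support that. Under Protocol 7.8.1, iron is started and stopped on ferritin and TSAT thresholds, with the dose left to local practice, so a reduction could come largely through fewer users. The SD ratio can then stay near or slightly above 1 and coverage near 95%. This stands. The exception is narrow, though: it needs a high user share, little variation among users, and an effect almost wholly through user share.

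**The confirmatory decision is largely safe.** A reader might also infer an inflated one-sided error rate. That needs equal mean use with unequal SDs, which does not follow from the argument that spread falls with dose. With no effect and identical distributions the error rate holds; one simulation gave 2.1% one-sided. If daprodustat raised use and spread together, the pooled interval would be conservative. Where coverage falls, the null is already false, and decisions barely change: in a proportional-reduction simulation, model-based and HC3 tests rejected in 90.1% and 88.9% of trials at a 20% reduction, and 99.8% for both at 30%. This stands.

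**Very short exposures are a separate matter.** They enter with full weight. As an illustration, 1000 mg within 7 treatment days is divided by 8 days under SAP 14.6.3.2 (stop date + 1 − start date + 1). That gives 1000 × 30.4375/8 = 3,805 mg/month and moves a 134-person mean by about 28 mg/month. A robust SE leaves that shift untouched, so the example is no argument for changing the variance. The supportive on- and off-treatment analysis already lengthens such denominators for people who stay in the study.

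**Unequal spread would be seen.** SAP 7.2.5.1 requires boxplots and SDs by arm. That is true, but these appear after unblinding, and nothing says what follows from them.

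**Conclusion.** The point holds in conditional form. SAP 7.2.5.1 has no protection against unequal residual variance on its one confirmatory secondary test, and 2:1 allocation makes the interval sensitive to it. If the daprodustat SD is 10% to 30% smaller, nominal 95% coverage is about 94% to 92%; at half the epoetin SD it is 89%. The SE is understated by about 3% to 11% over the first range and by 18% at the extreme. If the SDs are equal nothing is lost, and if the daprodustat SD is larger the interval is too wide.

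The SD ratios, user shares and coefficients of variation are all assumptions, since the documents give no IV iron SD or expected effect. The conclusion concerns the precision claimed for the effect estimate when the drug works. It is not a claim of inflated type I error, and the choice of ANCOVA on the mean is not itself wrong.

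**What to change.** Add one sentence to SAP 7.2.5.1 before unblinding: the SE, 95% CI and one-sided p-value for the treatment difference will use a heteroscedasticity-consistent variance (for example HC3) or a separate residual variance per arm. Estimand, covariates, alpha and testing order stay as they are. HC3 is the simpler choice because it leaves the point estimate exactly unchanged, whereas fitting a variance per arm reweights the data and can move it slightly. Use the same option in the supportive on- and off-treatment analysis so the two intervals are comparable.

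The cost is one procedure option. The interval widens by about 3.5%, 7.6% and 12% at SD ratios of 0.9, 0.8 and 0.7, which is the width it should have had, and is essentially unchanged when the SDs are equal. Robust variance brought simulated coverage back to about 94% to 95%.

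Optionally, and as a separate matter, add an ANCOVA weighted by time on treatment as a sensitivity analysis for very short exposures.

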### 7.3. Additional Secondary Efficacy Analyses

#### 7.3.1. Planned Secondary Efficacy Statistical Analyses

##### *Hgb Variability*

Secondary Efficacy Statistical Analyses: Hgb Variability
Endpoint / Variables

 
Hgb change from baseline to Week 52 (Hgb change from baseline to Week 52 will be tested for non-inferiority using the -0.75 g/dL margin used in the primary analysis)
 
% time Hgb in analysis range (10-11.5 g/dL) during the evaluation period (EP, Week 28 to 52) (% time Hgb in analysis range will be tested first for non-inferiority, then for superiority. The non-inferiority analysis will use a margin of 15% less time in range)
 
N (%) responders, defined as mean Hgb within the Hgb analysis range 10-11.5 g/dL during the EP
 

Model Specification

 
For the secondary analysis of Hgb change from baseline to Week 52, a mixed model repeated measures (MMRM) approach will be used with an unstructured covariance matrix to compare the difference in means between arms. The model will be fitted to Hgb data collected after baseline up to Week 52, excluding values collected during the stabilization period (Day 1 to Week 28). The model will include factors for treatment, time, prognostic randomization stratification factor (region, see Section 5.3), baseline Hgb and the baseline Hgb by time and treatment by time interaction terms. Analyses will be done with the MIXED procedure in SAS, using the Kenward-Roger option to estimate denominator degrees of freedom and standard errors. This analysis will be performed using all available Hgb values (on and off-treatment) and separately using evaluable Hgb values only (see Section 14.6.3). In the analysis using all available Hgb values, subjects who withdraw from the study before Week 52 are considered to be missing at random and in the analysis using evaluable Hgb values, subjects who permanently discontinue study treatment before Week 52 are assumed to be missing at random.
 
For the analysis of % time in range, the method by Rosendaal [Rosendaal, 1993] will be used to calculate the percentage of time (days) a subject's Hgb is below, within and above the Hgb analysis range of 10 to 11.5 g/dL during the EP (Weeks 28-52). A van Elteren test (stratified Wilcoxon rank sum test) will be used to compare the percentage of time in range between treatment arms, adjusting for treatment and the prognostic randomization stratification factor (see Section 5.3). This analysis will be performed using evaluable Hgb
 

values only. Hodges-Lehmann estimate of the treatment difference will be used to assess non-inferiority in % time in range.
 
 
For the Hgb responder analysis, mean Hgb during the EP will be defined as in the while on-treatment evaluable Hgb supportive analysis (Section 14.6.3). Responders will be subjects with a mean Hgb during the EP that falls within the Hgb analysis range of 10-11.5 g/dL. A Cochran-Mantel-Haenszel (CMH) chi-squared test, adjusting for treatment and the prognostic randomization stratification factor (region as randomized, see Section 5.3), will be used to compare the number and % of responders between the treatment groups.
 


Model Results Presentation

 
For the MMRM analysis of change from baseline in Hgb, an LSMEANS statement will provide adjusted treatment group means and standard errors and a point estimate and two-sided 95% confidence interval for the adjusted mean treatment difference (daprodustat - rhEPO) at Week 52. The one-sided non-inferiority p-value for this test will be calculated.
 
For the responder analysis, the number and percentage of subjects with mean EP Hgb above, within and below the Hgb analysis range will be summarized by treatment group.
 
For the responder analysis, the number and % of responders by treatment group, difference in response rate (Dapro – rhEPO) and two-sided 95% CI will be provided along with the one-sided CMH p-value for the treatment group comparison.
 
The % time Hgb is above, in and below the Hgb analysis range (10-11.5 g/dL) during the EP will be summarized using mean, standard deviation, minimum, P25, median, P75, and maximum by treatment group.
 
For the percent time Hgb in analysis range for each treatment group, the stratified Mann-Whitey estimate of the treatment difference (daprodustat - rhEPO) and associated two-sided 95% CI [Kawaguchi, 2011] will be presented in addition to the one-sided superiority p-value from the van Elteren test. Hodges-Lehmann estimate of the treatment difference (daprodustat-rhEPO) and associated two-sided 95% CI will be presented.
 

Model Results Interpretation

 
For the MMRM analysis of change from baseline in Hgb, the NI margin used in the primary analysis of Hgb (-0.75 g/dL) will be used for reference in this comparison. Thus generating support for non-inferiority if the lower bound of the two-sided 95% CI is above -0.75 g/dL.
 
For the responder analysis, the one-sided CMH p-value will be compared to 0.025 to assess nominal significance.
 
For the percent time in range analysis, a NI margin of -15% will be used as a reference in this comparison, thus generating support for non-inferiority if the lower limit of the two-sided 95% CI of Hodges-Lehmann estimate is above -0.15. If non-inferiority is established, nominal superiority will be achieved if the one-sided p-value is < 0.025
 

Subgroup Analyses


 
Subgroup analyses will be performed for all Hgb variability endpoints, using the region and hyporesponder subgroups only (described in Section 5.3 & Section 5.4), in a method similar to that described for the subgroup analyses of the primary and principal secondary analyses
 

CONFIDENTIAL

204837

*Time to Rescue*

Secondary Efficacy Statistical Analyses: Time to Rescue
Endpoint / Variables

 
Time to stopping study treatment due to meeting rescue criteria
 

Model Specification

 
The Cox Proportional Hazards model will adjust for the following baseline categorical values: 
 
Treatment
 
Region (as randomized, see Section 5.3 & Section 5.4.1)
 
 
 
Confidence intervals for the rate per 100 person-years will also be reported. For within-group rates, the two-sided 95% CI will be obtained using an exact Poisson method. For difference in rates between treatments, the two-sided 95% CI will be constructed with a Normal approximation using Wald's method [Liu, 2006].
 
Analysis will include only those efficacy endpoints occurring within the time period for treatment discontinuation. Calculation of time-to-event or censoring is described in further detail in Section 14.6.3.
 
Time to stopping study medication due to meeting rescue criteria is defined as the time from Randomization until the date on which a subject permanently stops study medication due to meeting criteria for rescue.
 

Model Results Presentation

 
Summaries will include (see Section 14.6.3): 
 
the number and percentage of subjects meeting evaluation criteria for rescue and the number of occurrences (events),
 
the number and percentage of subjects unable to be evaluated for rescue, and
 
the number and percentage of subjects meeting rescue.
 
 
 
The analysis model results presentation: 
 
Number (%) of subject permanently stopping study treatment due to meeting rescue criteria within each treatment arm
 
Number (%) of subject censored
 
Incidence rate per 100 person-year and the associated two-sided 95% confidence intervals for each treatment arm
 
Hazard ratio and the associated two-sided 95% confidence interval
 
One-sided p-value for the test of superiority of daprodustat vs rhEPO
 
Absolute rate difference per 100 person-year and the associated two-sided 95% confidence interval
 
 
 
A Kaplan-Meier plot of time to stopping study treatment due to meeting rescue criteria will be produced.
 

Model Results Interpretation

 
One-sided p-values will be compared to 0.025 to assess nominal significance
 

Subgroup Analyses

 
Subgroup analyses will be performed for the time to rescue endpoint using the hyporesponder subgroup only (described in Section 5.4). Cox Proportional Hazards model will be adjusted for the covariates used in the original analysis (region, treatment), hyporesponder subgroup, and treatment by subgroup interaction.
 

CONFIDENTIAL

204837

